12.6 Concomitant clinical management and co-interventions

Women with severe early-onset FGR are also at high risk of developing preeclampsia. In this occurrence, additional therapies, surveillance and possibly delivery indicated on maternal rather than fetal grounds.

All women with severe early-onset FGR, regardless of co-existing preeclampsia, will require intense fetal surveillance, possible in-patient stay and early delivery. Once the fetus has reached an appropriate gestational age and size (and is deemed viable) corticosteroids will be administered to improve fetal lung maturity and once delivery is planned magnesium sulphate therapy will be considered for perinatal neuroprotection per institutional guidelines. These additional therapies and management will be provided at the discretion of the clinician/trial centre caring for each woman. Trial investigators will collect data regarding these co-interventions.

12.7 Outcome data collection

The researcher will collect relevant data regarding pregnancy outcomes from the maternal clinical record (hard copy and online hospital databases). Neonatal and child (up to 3 years) outcome data will be collected from the hospital records (hard copy and online hospital records) from the time of birth up to 3 years corrected age. Consent will also be sought to access longer term childhood outcome data, such as educational performance. If participants are enrolled in concurrent studies where the same assessments are involved, or if the clinical team has flagged for particular common assessments to be complete, patient data will be shared between research and/or clinical teams to minimise the inconvenience for the

participants. The research team will seek formal consent for this data sharing arrangements from these participants.

12.8 Data collection and record

At the time of recruitment, each participant will be assigned a unique trial code. Hereafter, all data collected from the participant will be used and then stored only with this unique code associated with it. All electronic data, including GMA assessments using Baby Moves, will be stored on a RedCap database, that is password protected with restricted access limited only to the named principal investigators and the trial researchers. Likewise, any hard copies of material bearing participant information e.g. signed Consent Forms or Case Report Forms will be stored securely e.g. locked filing cabinet with restricted access, limited only to the named principal investigators and the trial researchers.

Upon trial completion, all data and records will be stored in the Department of Obstetrics and Gynaecology, Monash University, or another off-site secure location, and participating sites will also store their site specific trial related records for the duration of >25 years.

The principal investigator will be responsible for data storage, retention and destruction. Should the principal investigator leave the institution prior to the trial completion or the 25 years has been reached, the responsibility for record retention, storage and destruction will be passed to another individual nominated by the PI to assume responsibility.

12.9 Disposal of remaining tissue samples and optional future use

At the time of consent, participants will be given an option to agree to any remaining tissue(s) being stored and used, in any future related pregnancy/birth FGR related research project for which HREC approval is sought and given. The PI&CF clearly states that this is an optional component of the now proposed research project and does not impact upon (current) trial participation should the potential participant choose to decline this option for the future use of their tissue(s).

If a participant chooses to take part in the optional component of the research project and permit donation of any remaining tissues to any future related FGR research project, the PI&CF states that the future use may involve genetic testing. Specifically, "*The tissue(s) that you donate for any future, related FGR research could one day be used for genetic testing to learn about the role genes play in FGR. Genes are the basic "instruction book" for the cells that make up our bodies and may be passed on from generation to generation within families. Since the significance of any future genetic tests is not known for you, we will not release the results of any genetic testing nor will the results be used in the planning of your clinical care, or that of your child*".

For those participants who choose not to take part in the optional component and donate tissue(s) to any future, FGR related research projects, following the laboratory analyses of samples for this project, any remaining tissue(s) will be disposed of as clinical waste in line with site specific institutional policies on the handling and disposal of human tissues.

13. ASSESSMENT OF COMPLIANCE WITH THE TRIAL INTERVENTION

The trial intervention will be prescribed, as per protocol, on a fortnightly basis by the named investigators who hold medical doctor (MD) status, full registration with the relevant regulatory body e.g. AHPRA or the medical council of NZ and are employed at the trial institution. Subsequently, the prescription will be dispensed and stored according to the institution's policy for the handling and storage of tablets to be administered to participants in a clinical trial.

Participants will be asked to complete a trial intervention Compliance Log and return all containers including any remaining tablets, to the researcher to determine compliance with the administration of the trial intervention.

14. OUTCOME MEASURES

14.1 - Primary Outcome

Improved neurodevelopmental performance at 2 years of life among survivors of early onset FGR.

The ability of melatonin to protect the fetal brain in the setting of severe early-onset fetal growth restriction will be assessed by multiple assessments across the first 2 years of life. The trial is powered to detect a difference in neurodevelopmental performance at 24-36 months corrected age on the Bayley-4. Other tools of assessing brain development and neurocognitive performance will also include GMA and MRI at term, GMA again at 3-months corrected age and ITSEA at 24-36 months corrected age. These assessments will also be stratified depending on the fetal gestation and fetal Dopplers at the time of FGR diagnosis, with outcomes for those <28 weeks and between 28-31+6 weeks compared as a sub-analysis. Total mortality will be compared between melatonin and placebo.

14.2 - Secondary Outcomes

- Assessment of drug safety and tolerability: Maternal side effect profiles experienced, such as symptoms of drowsiness, abdominal cramps, flushing, migraines, gastrointestinal disturbance. This information will be collected from the participant medication diary.
- Maternal end-organ performance monitored through haematological and biochemical tests
- Fetal effects through assessing ultrasound parameters of fetal biometry (HC, BPD, AC and FL) and wellbeing (AFI, Doppler indices).

15. STATISTICAL ANALYSES

Outcome measures between the melatonin treatment and placebo groups will be analysed on an intention to treat basis. GMA, MRI, ITSEA and Bayley-4 scores will be compared between

groups using parametric or non-parametric testing, depending on their distribution. Simple regression analyses will be performed to explore relationships with functional outcomes.

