7. SAMPLE SIZE AND POWER CALCULATIONS

The required sample size has been calculated to detect if melatonin supplementation affords a clinically relevant difference in neurodevelopmental outcomes among survivors. An increase of 4-5 quotient points in the Bayley-4 Cognitive scale has been deemed sufficiently clinically meaningful to drive changes in health policy previously ⁵⁵. Power analysis shows that 69 participants per group will allow the detection of a difference in the Bayley-4 cognitive score of 5 points between the two groups, with a power of 90% and an alpha level of 0.05, using 2sided T test for comparison. This assumes a standard deviation of 9 ⁶ and that, on average, the growth restricted infant has been shown to have a cognitive score 5 points lower than the healthy preterm infant and 8 points lower than the healthy term infant⁶. Typically, the Bayley-4 score has a standard deviation of 15, however reduced variability has been seen in the FGR population and this has informed the standard deviation used here. Among pregnancies complicated by early onset FGR a perinatal loss rate of ~15% is commonly observed ^{41,56}. Allowing for a perinatal loss rate of 15%, an extra 42 women will be recruited. Assuming an additional 5% loss to follow-up rate, we will aim to recruit an extra 14 participants.

This trial also aims to assess whether the impact of melatonin is different at different gestational ages. Therefore, a sub-analysis will be undertaken to compare those with early onset FGR identified <28 weeks' gestation to those with late-onset FGR identified between 28-31+6 weeks gestation. To ensure that this sub-analysis is adequately powered, participants recruited will be randomized to either melatonin or placebo based on their gestational age at diagnosis. Therefore, recruiting 83 participants per group will see the overall trial aiming to recruit 332 participants (see figure 1).

[figure not shown]

Figure 1: Flowchart of Participant Assignment to Trial Arms.

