9. RANDOMISATION

Randomisation will be via an on-line computerised randomisation service. Randomisation will occur on a 1:1 ratio of melatonin to placebo with the goal of 83 participants randomized to each of the two trial arms stratified by gestational age at recruitment and the presence or absence of abnormal Dopplers. At the time of recruitment, each participant will be assigned a unique trial code. Subsequently, all data and tissue samples collected from the participant will be stored only with this associated code. Thus, all data and tissue samples are deidentified at the point of collection, but with the capability to re-identify them in the future for data verification, research audit or safety (e.g. needle-stick injury).

Furthermore, it will be possible to break the randomization code and reveal treatment group if necessary, such as in the event of a potential treatment-related serious adverse event occurring.

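### Section 15 lets the score distribution choose the test for an outcome that Section 7 sized as a mean difference; separately, the gestation strata are dated at diagnosis in two sections and at recruitment in another

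*Protocol*

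**What the plan says.** **Test.** Protocol Section 7 plans to detect "a difference in the Bayley-4 cognitive score of 5 points between the two groups", with 90% power and alpha 0.05, "using 2sided T test for comparison", assuming an SD of 9. Section 15 covers GMA, MRI, ITSEA and Bayley-4 scores in one sentence and compares them between "groups using parametric or non-parametric testing, depending on their distribution". It does not treat the primary outcome separately and does not say how the distribution will be judged.

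**Primary measure.** Section 12.5.3 names the Bayley-4 Cognitive score at 24-36 months corrected age as primary. Section 14.1 refers to the Bayley-4 without naming a domain. It also places GMA, MRI, ITSEA and total mortality under the primary outcome heading, although it sets the first three apart as other tools.

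**Strata.** Section 7 says that "participants recruited will be randomized to either melatonin or placebo based on their gestational age at diagnosis". Section 9 says that randomisation is "stratified by gestational age at recruitment and the presence or absence of abnormal Dopplers". Section 14.1 stratifies the assessments by gestation and Dopplers at FGR diagnosis. Section 12.1 collects earlier Dopplers only where they were done. Section 12.4 takes the trial's own Dopplers on the day of recruitment or up to 3 days before.

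**Numbers.** Section 7 states that "recruiting 83 participants per group will see the overall trial aiming to recruit 332 participants". Section 9 sets out "with the goal of 83 participants randomized to each of the two trial arms", in the same sentence as the strata.

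**The concern.** A t test and a rank test answer different questions. The first concerns the difference in means, which is what Section 7 planned for. The second concerns whether a child in one arm tends to score higher than a child in the other. If melatonin moved every child by the same amount, the two would agree closely. If it worked mainly by preventing poor outcomes in a minority, the mean would move more than the middle of the distribution, and a rank test could miss much of the effect. That pattern is plausible here, because Sections 2.1 and 4.1 describe brain injury and impairment in some of the children. Section 15 leaves the choice until the scores have been seen.

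The stratum wording raises a separate question. A woman diagnosed before 28+0 weeks and recruited after it belongs to the early group under Sections 7 and 14.1 but to the late group under Section 9. The factor used to randomise her and the factor used in the sub-analysis would then differ.

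**Working it through.** **1. Reproduce the plan's figure.** Inputs from Section 7: difference 5, SD 9, two-sided alpha 0.05, power 0.90.

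n per group = 2 × [9 × (1.960 + 1.282) / 5]² = 68.09, rounded up to 69. The t-test solution is 69.06, and power at 69 is 0.900.

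Total: 4 × 69 = 276. Perinatal loss: 276 × 0.15 = 41.4, taken as 42. Loss to follow-up: 276 × 0.05 = 13.8, taken as 14. Sum: 276 + 42 + 14 = 332 = 4 × 83. The stated numbers therefore follow from a comparison of means.

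**2. Evaluable numbers under the plan's own loss rates.** 332 × 0.85 × 0.95 = 268.09, which is about 134 per arm or 67 per arm within a gestation stratum. T-test power for 5 points at SD 9 is 0.995 and 0.891 respectively. The simulations below use the planning figures, 138 (= 2 × 69) and 69.

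**3. What the choice of test does.** Section 15 gives no rule, so one is assumed: Shapiro-Wilk on the residuals, then a rank-sum test if p < 0.05 and a t test otherwise. The score shapes are also assumed. There were 4,000 simulated trials per case.

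Type I error under the rule at 138 per arm is 0.050 (normal scores) and 0.054 (10% of both arms 20 points lower). At 69 per group it is 0.049 and 0.045.

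Power when the true mean difference is 5.0 points:

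| Assumed source of the 5 points | Median difference | 138 per arm: t test / rule | 69 per group: t test / rule |
|---|---|---|---|
| Normal scores, every child shifts by 5 | 5.0 | 0.996 / 0.996* | 0.900 / 0.900 |
| 10% low scores in both arms, every child shifts by 5 | 5.0 | not run | 0.905 / 0.950 |
| Low scores 20% v 5%, plus a 2-point shift: 0.15 × 20 + 2 | 3.6 | 0.997 / 0.985 | 0.890 / 0.820 |
| Low scores 25% v 0%: 0.25 × 20 | 2.7 | 0.998 / 0.940 | 0.923 / 0.730 |

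A low score is one lowered by 20 points. *From a companion run that applied the pre-test in each arm.

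**4. Strata, side by side.**

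| Section | Gestation taken at | Dopplers taken at |
|---|---|---|
| 7 | diagnosis | not mentioned |
| 9 | recruitment | time not stated |
| 14.1 | diagnosis | diagnosis |
| 12.1 and 12.4 | – | earlier scans where done; trial scan at recruitment or up to 3 days before |

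The protocol gives no interval between diagnosis and recruitment, so the number of women who change stratum cannot be computed. For illustration only: the window from 23+0 to 31+6 weeks is 63 days. If diagnoses were spread evenly over it, each day of lag would move 1/63 = 1.6% of women, or 332/63 = 5.3.

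**The case against.** The strongest reply is that little is lost where it matters most. On the pooled comparison at the planned 5 points, power under the rule did not fall below 0.94 in any case run, and in some cases the rule does better than the t test. The steepest loss in the table, to 0.73, is at 69 per group. It also needs arm SDs of √(6.3² + 20² × 0.25 × 0.75) = 10.7 and 6.3, where Section 7 assumes a common 9. A sharp pooled loss (0.78 to 0.56 at 138 per arm) appears only for a 3-point effect, which the protocol did not plan for. All of this is fair. It shows that the case rests on an unfixed target quantity and not on a demonstrated loss of power.

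A second reply is that such detail belongs in a statistical analysis plan. That holds for silence, but Section 15 is not silent. A later plan that fixed the mean difference would depart from it, and one that followed it would inherit the ambiguity.

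Three stronger readings are tempting, and the protocol does not support them:

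- **That no primary domain is defined.** Section 12.5.3 names the Cognitive score and Section 7 sizes on it. Section 14.1 is only out of step with them.
- **That the primary might be confined to a stratum, or that the trial might stop at 166 women.** Section 10.1 randomises to two groups and Section 15 compares those two. Section 7 calls the gestation comparison a sub-analysis and states 332. Section 16.7.4 plans a safety report after 200 recruits. The 83 in Section 9 can be read as per arm within each gestation stratum.
- **That the stratum mismatch invalidates randomisation.** Allocation is random under either definition.

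**Conclusion.** The point holds in a limited form and should be fixed. Section 15 does not carry forward the comparison of means on which Section 7 rests, so the primary analysis may test a different quantity from the one sized. A reader might infer a false-positive problem; the simulations give 4.5-5.4% and do not support that. A reader might also infer that the trial is underpowered; at the planned 5 points with 138 per arm, power stays at 0.94 or more. The exposure is larger at 69 per group, with power from 0.95 down to 0.73. It depends on the assumed score shapes and pre-test, and it can go in either direction.

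The diagnosis/recruitment mismatch is a plain contradiction between sections. Its consequence is an ambiguous sub-analysis and an ambiguous adjustment factor, not bias. Its size is unknown.

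**What to change.** - **Section 15:** fix the primary analysis as the between-arm difference in mean Bayley-4 Cognitive score at 24-36 months corrected age, with 95% CI. Estimate it by linear regression on arm plus the factors actually used at randomisation (gestation stratum and abnormal Dopplers). Keep any rank test as a sensitivity analysis only.
- **Sections 7, 9 and 14.1:** reconcile to one gestation definition and one Doppler time point, checked against what the randomisation service used. Use the same definition for the <28 / 28-31+6 week sub-analysis.
- **Minor wording:** name the Cognitive score in 14.1, in line with 12.5.3. List GMA, MRI, ITSEA and total mortality as secondary. Say in Section 9 that 83 is per arm within each gestation stratum.
- **If evaluable numbers are quoted:** use about 134 per arm (99.5% power for 5 points at SD 9) and 67 per arm within a stratum (about 89%).

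The cost is wording and one check with the randomisation service, made before unblinding. No new data are needed and N = 332 is unchanged.

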10. TRIAL STUDY GROUPS

10.1 – Trial Study Groups

Once informed, written consent has been obtained, participants will be stratified by gestational age. Hereafter, participants will subsequently be randomized into one of two groups to receive the trial intervention, either:

1. Melatonin
10mg melatonin tablets, administered three times a day (tds) (a total daily dose of 30mg per day) **or**
2. Placebo
Visually identical placebo tablets containing no active ingredient, administered three times a day (tds)

Participants, their healthcare providers and the research team will be blinded to the trial intervention the participant has received throughout the trial and during follow-up of the children until all participants have completed all the stages of the trial as per protocol.

10.2 – Drug Supply and Storage

Melatonin 10mg tablets with a Certificate of Analysis will be sourced by Akesa Pharma (Melbourne, Australia). A matched placebo will then be produced by the Pharmaceutical Packaging Professionals (Port Melbourne, Australia), who will repack all trial medication to maintain blinding and manage its storage and distribution. Trial medication will be supplied in bottles containing 42 tablets to cover trial medication for a 2-week period. Trial medication will then be dispensed to participating sites designated trial pharmacies for dispensing to the individual trial participants on a fortnightly basis.

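### Randomisation is stratified by gestational age and Doppler status, but the stated comparison is a plain two-group test; if the strata predict the score, its interval and p-value are conservative.

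*Protocol*

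**What the plan says.** - **Randomisation.** Section 9 allocates 1:1, "stratified by gestational age at recruitment and the presence or absence of abnormal Dopplers". Section 10.1 says only that "participants will be stratified by gestational age" and does not mention Dopplers. Section 7 ties randomisation to gestational age at diagnosis.
- **Analysis.** Section 15 sets an intention-to-treat comparison of GMA, MRI, ITSEA and Bayley-4 between "groups using parametric or non-parametric testing, depending on their distribution". It mentions regression only for exploring relationships with functional outcomes.
- **Sample size.** Section 7 states that "69 participants per group will allow the detection of a difference in the Bayley-4 cognitive score of 5 points between the two groups". Power is set at 90% and two-sided alpha at 0.05, and the method behind the figure is given as "using 2sided T test for comparison". The SD taken for the calculation is 9; the same section gives 15 as the usual SD of the scale.
- **By-stratum look.** Section 14.1 adds: "These assessments will also be stratified depending on the fetal gestation and fetal Dopplers at the time of FGR diagnosis". It then describes the comparison of the two gestational-age bands as a sub-analysis.

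**The concern.** Stratified randomisation balances the arms on the chosen factors, so differences between strata no longer contribute to the chance error of the treatment difference. An ordinary two-sample test does not know this. It estimates the error from the full spread of scores, between-stratum spread included, and so overstates it. The method in Section 15 therefore does not match the design in Section 9.

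At stake is the calibration of the primary result. The 95% interval would be wider than it needs to be and the test would run below its nominal 5%. Precision that the stratification has already bought would go unused. There is a second, smaller cost. If the non-parametric route is taken, the result is not an estimate in Bayley-4 points, which is the unit of the target difference in Sections 7 and 12.5.3.

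**Working it through.** **Inputs from the protocol (Section 7).** Difference 5 points, SD 9 (usual SD 15), two-sided alpha 0.05, power 90%, 1:1 allocation.

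**The plan's own figure.** n per group = 2 × SD² × (1.960 + 1.282)² / difference² = 2 × 81 × 10.51 / 25 = 68.1, rounded up to 69. This reproduces the stated 69. Four gestational-age-by-arm cells give 4 × 69 = 276 evaluable, or 138 per arm. Adding 42 (276 × 0.15 = 41.4) and 14 (276 × 0.05 = 13.8) gives 332 = 4 × 83, as stated.

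**Assumed input.** R2 is the share of score variance explained by the strata. The protocol gives no value, so I use 0.05, 0.10 and 0.20. I also assume that the arms are balanced within strata; the protocol states no blocking method.

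**Width of the standard error.** The true SD of the difference is the unadjusted SE × √(1 − R2), so the unadjusted SE is too wide by the factor 1/√(1 − R2). The unadjusted test's type I error is 2 × [1 − Φ(1.96/√(1 − R2))].

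| R2 | SE ratio | Type I error, formula | Type I error, simulated |
|---|---|---|---|
| 0.05 | 1.03 | 4.4% | 4.3% |
| 0.10 | 1.05 | 3.9% | 4.1% |
| 0.20 | 1.12 | 2.8% | 3.0% |

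The simulation used 272 evaluable children, SD 9, balanced arms in four strata and 8,000 runs per setting. At R2 = 0.20 the mean unadjusted SE was 1.09, against a true SD of 0.98 to 0.99 and an adjusted SE of 0.98. The adjusted model's type I error stayed near 5%.

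**Power for a 5-point difference.** Same simulation, unadjusted against adjusted. The sizes 272 and 136 approximate the planned 276 and 138.

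| Setting | R2 = 0.05 | R2 = 0.10 | R2 = 0.20 |
|---|---|---|---|
| Whole trial (272), SD 9 | 99.7 vs 99.8% | 99.8 vs 99.9% | 99.8 vs 99.9% |
| One gestational-age stratum (136), SD 9 | 90.3 vs 91.3% | 91.0 vs 92.7% | 91.9 vs 94.7% |
| Whole trial (272), SD 15 | 78.3 vs 79.6% | 79.2 vs 82.2% | 80.3 vs 86.2% |

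The loss is nil to the eye in the first row, 1 to 3 points in the second and 1 to 6 points in the third. Within one gestational-age stratum the age band is fixed, so R2 can come only from Dopplers (or from age within the band). An overall effect of 3 points at SD 9 has the same standardised size as 5 points at SD 15 (3/9 = 5/15), so the third row also shows roughly what happens with a smaller effect.

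If the strata do not predict the score, R2 = 0 and nothing is lost.

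**The case against.** The best reply is that covariates commonly belong in the SAP, which is not shown. Section 15 is a short outline that never says the comparison is unadjusted, and sizing on a t test does not bar an adjusted analysis. This has some force. But Section 15 is not silent: it names a method for the primary outcome, and that method leaves out the randomisation factors. An SAP with an adjusted model would have to depart from it. Nor does Section 14.1 settle the matter. Its wording is loose, but it reads as an additional look by stratum.

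The second reply is that the error is on the safe side: type I error stays below 5% and there is no bias. That is correct and limits the seriousness.

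A reader might infer more than the protocol supports:

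- **A material loss of power in the main comparison.** At 5 points and SD 9 there is none worth naming.
- **A need for 18% more children.** If each factor is assumed to shift the mean by 5 points, with equal strata, R2 = 2 × 2.5²/81 = 0.154 and 1/(1 − 0.154) = 1.18. That describes interval width. For power at 3 points the unadjusted test would need about 300 children instead of 268, or 12%, because stratified allocation has already reduced its true error. The 5-point shift is itself borrowed from the contrast of growth-restricted with healthy preterm infants, not from a contrast between strata.
- **Proof in Section 4.1 that development is worse below 28 weeks.** That section speaks of perinatal mortality by gestation at birth, not of Bayley scores among survivors by gestation at entry.
- **A need for a site term.** Section 9 does not stratify by site, and the protocol text at hand does not show that Bayley-4 assessors differ by site. Such a term is a preference.

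**Conclusion.** The point holds in a limited form. The stated primary comparison does not use the factors on which randomisation is stratified, and it is conservative to the extent that two conditions are met: the strata predict the score, and the arms are balanced within them. The protocol quantifies neither. For R2 between 0.05 and 0.20 the standard error is 3 to 12% too wide and type I error is about 4.3 to 3.0%.

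The power cost depends on the setting. It is negligible for the overall comparison at the protocol's own inputs, and a few points for smaller effects, an SD near 15, or a single gestational-age stratum. The result would not be invalid. The change is still worth making, because it restores nominal error rates, tightens the interval and costs almost nothing.

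**What to change.** In Section 15, state that the primary analysis is a linear model of the Bayley-4 Cognitive score on treatment, with the gestational-age and Doppler strata used at randomisation as covariates, and that the adjusted mean difference is reported with its 95% CI. Use the same two factors for ITSEA, MRI and GMA, with a model suited to each outcome type. Section 7 can keep the t-test calculation, described as a conservative approximation.

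Reconcile the strata before writing this. Section 9 names gestational age at recruitment and Dopplers, Section 10.1 gestational age only, Section 7 gestational age at diagnosis, and Section 14.1 gestation and Dopplers at diagnosis. The covariates should be the values actually entered at randomisation.

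The cost is a sentence in Section 15, matching text in the SAP and small wording changes in the other sections. Gestational age and Doppler findings are already collected, so no further participants or data are needed. The change should be made before unblinding.
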